6.5.8. Exposition *in utero*

Three pregnancy tests are planned during the study: on D-1, prior to starting treatment, at hospital discharge and at the 3-month follow-up visit. Among girls \geq 12 years of age, i.e. of child-bearing potential, only those who have a negative result on the pregnancy test on D-1 will be eligible to participate in the study.

The Investigator must report any pregnancy that occurs during the observation period of the study, or that is diagnosed before or at the 3-month follow-up visit, using the appropriate pregnancy reporting form. This must be done irrespective of whether an AE occurred or not. If known, the due date must be specified.

The Investigator will monitor the patient until the term of the pregnancy, i.e. full term or preterm in the event of a miscarriage. The Investigator will provide information on the outcome of the pregnancy using the pregnancy follow-up reporting form.

A physician, preferably a paediatrician, should examine the infant at birth and submit a report using a pregnancy follow-up reporting form. The Investigator will offer the parents follow-up on infants exposed to the IP *in utero* until they reach 24 months of age. As far as possible, stillborn infants should be examined by a physician to assess the cause of death.

6.5.9. Follow-up on Adverse Events

All AEs must be followed until resolution, or until the Investigator considers them to be "chronic" or "stable", or until the patient's participation in the study ends, i.e. until the final report is completed for the study in which the patient was participating.

If the AE is a laboratory abnormality with a toxicity grade \geq 3, the test must be repeated 2 to 4 days later, and then at regular intervals until the parameter reaches toxicity grade \leq 1, or until it returns to the baseline level (see Baseline Assessment).

In addition, all SAEs and all events that the Investigator (and the Coordinating Investigator or the monitor, as needed) considers as possibly related to the IP must continue to be followed even after the end of the patient's participation in the study. Such events should be followed until their resolution, or until the Investigator considers them as "chronic" or "stable." The resolution of such events must be documented in the CRF, and if they are SAEs, on an SAE follow-up form.

7. Study Duration

The enrolment period is expected to last up to 22 or 24 months. The treatment period will last 10 days.

Each patient's participation will last approximately 19 months and will include:

- pre-treatment period (pre-screening and screening, treatment of concurrent disease)
- treatment period of 10 days
- hospitalisation for 3 to 8 days after treatment
- out-patient follow-up for 12 months
- additional follow-up until 18 months.

The total duration of the study is expected to be 36 months.

8. Withdrawal Criteria

8.1. Rules for Temporary Interruption of Treatment

Temporary interruption of treatment will not necessarily lead to withdrawal of the patient from the study. In some cases, treatment may be interrupted for a maximum of one day, i.e. one missed dose of fexinidazole, and treatment will therefore be delayed. Treatment may be reintroduced at the discretion of the Investigator responsible for the patient. One additional day of treatment will be added to make up for the missed dose. The patient should continue the visits and study procedures as planned, taking into account the delay. The reasons for interrupting treatment must be recorded in the appropriate source documents and in the CRF.

8.2. Rules for Definitive Discontinuation of Treatment

The Investigator will discontinue the IP in the following cases:

- Severe skin reaction;
- ALAT or ASAT exceeding 8 x ULN;
- ALAT or ASAT exceeding 3 x ULN accompanied by total bilirubin exceeding 2 x ULN;
- ALAT or ASAT exceeding 3 x ULN accompanied by fatigue, nausea, vomiting, right upper quadrant pain or tenderness, fever, rash and/or eosinophilia exceeding 5%;
- QTcF interval ≥ 500 msec prior to intake of fexinidazole on D2, D3, D4 or D4H23), confirmed by a second ECG recorded after the patient has been in the resting position for at least 10 to 20 min;
- Any condition that, in the opinion of the Investigator, requires treatment discontinuation for medical reasons.

If a patient is withdrawn from the study before the end of treatment, the physician will make all necessary arrangements to ensure that s/he receives appropriate treatment for the condition in question.

8.3. Patient Withdrawal from the Study and Replacement of Patients

A patient may be withdrawn from the study in the following cases:

- withdrawal of consent by the patient or his/her legal representative;
- study termination by the Sponsor.

If the patient or his/her legal representative withdraws his/her consent, no further evaluations will be performed, with the exception of safety data, which must be collected whenever possible.

Data collected prior to withdrawal of the patient will be taken into account in the efficacy and safety analyses.

If a patient decides to withdraw from the study, the reason must be recorded in the CRF. If a patient is withdrawn from the study due to an AE, all measures must be taken as needed to clearly document the outcome of the AE. Patients withdrawn from the study will not be replaced.

8.4. Patients Lost to Follow-up

If a patient does not attend a protocol-planned visit, all necessary measures must be taken to contact him/her. In all cases, all necessary measures must be taken to document the outcome of the patient's condition, if possible.

9. Data Analysis and Statistical Methods

A full Statistical Analysis Plan (SAP) will be prepared prior to database lock. It will provide a detailed description of the statistical methods.

9.1. Sample Size Determination

Determination of the sample size was based on the primary analysis (see Section 9.8.1 Primary Efficacy Analysis, p 61). With a sample size of 125 patients, the probability of rejecting H_{0A} ($\pi \le 0.8$) is 97.5% if the true success rate is 92% with a one-sided type-I error of 0.025. The probability of rejecting H_{0B} ($\pi \ge 0.92$) is also 97.5% if the true success rate is 80% with a one-sided type-I error of 0.025. The statistical power achieved is slightly higher than the desired power, and the alpha value obtained is slightly lower than the desired value, due to the discrete distribution of the population. The sample size may be 126 patients who received at least one dose of fexinidazole if two patients are recruited simultaneously at the time of study discontinuation. If the sample size exceeds 126 patients, there is a risk of simultaneously rejecting both H_{0A} and H_{0B}. The sample size should not be less than 125 in order to avoid the risk of not rejecting either hypothesis.

9.2. Handling of Missing Data and Patients Lost to Follow-up

The primary endpoint is the outcome, i.e. success or failure, of treatment at the 12-month visit. If the outcome at the 12-month visit is missing, the **primary method of imputation** will consist in imputing a probable success (considered as a success) to patients who attended the visit but who refused the lumbar puncture planned for the visit, who showed no signs or symptoms of HAT at 12 months, who did not subsequently report any symptoms of relapse and for whom the outcome was considered as favourable at the last available assessment (42). If these criteria are not fulfilled, the patients will be considered as treatment failures. The outcome for patients lost to follow-up from the 12-month visit onwards will also be considered as a failure.

Two additional methods for imputing missing data will be used.

The **second method** will consist in imputing failure if there is no lumbar puncture at 12 months or later.

In the **third method**, missing data will not be imputed. All patients for whom an assessment is available at a given timepoint will be included in the estimate of the success rate at that timepoint. If a value is missing at an intermediate visit,

followed by a success or a failure at one of the subsequent visits, the status at the subsequent visit will prevail over the status at the intermediate visit. In the Kaplan-Meier approach, the observation is censured at the first missing outcome, provided that all subsequent outcomes are also missing.

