2.2. Study Endpoints

2.2.1. Primary Efficacy Endpoint

The primary efficacy endpoint is the outcome, i.e. success or failure, observed at the test-of-cure (TOC) visit, 12 months after the end of treatment (EOT).

Success at 12 months, adapted from WHO criteria (54), is defined as:

- Patient cured, i.e.:
 - o patient alive,
 - AND no evidence of trypanosomes in any bodily fluid,
 - o AND CSF WBC ≤ 20/μL.

A patient with no evidence of trypanosomes in any bodily fluid, but with CSF WBC > $20/\mu$ L, or who, in the opinion of the Investigator, requires rescue treatment will be considered as a probable relapse.

Patients lost to follow-up and retrieved after 12 months or patients who refuse to undergo lumbar puncture at 12 months will be considered as patients probably cured, i.e. successes, if they have no clinical signs or symptoms suggestive of HAT or if their symptoms can be clearly attributed to another aetiology, provided that the outcome was favourable at the last available assessment of HAT (6-month visit or subsequent unscheduled visit). If a patient is not assessed, i.e. has no lumbar puncture, at 12 months, but has a lumbar puncture or physical examination subsequently or at 18 months, the outcome at the latter visit will prevail over that at 12 months.

Patients who die due to any cause, patients lost to follow-up and not retrieved, and patients who refuse to undergo lumbar puncture at 12 months and whose clinical outcome had previously been assessed as unfavourable, i.e. probable relapse, will be considered as failures.

The prinicipal visit for assessment of the efficacy endpoint, i.e. success or failure, was set at 12 months after the EOT because the relapse rate between 12 and 18 months is very low and highly consistent across the various treatments administered to patients with stage-2 HAT (historical data). The success rate for melarsoprol was 74.84% at 12 months and 73.71% at 18 months, i.e. a relapse rate of 1.1% (n=3477), (61). The success rate for effornithine was 90.3% at 12 months and 89.1% at 18 months, i.e. a relapse rate of 1.2% (n=743), (61). The relapse rate for NECT was 1.4% (n=143) between 12 and 18 months after the EOT (43). Consequently, the overall relapse rate between 12 and 18 months after the EOT is around 1.2% for patients with stage-2 HAT, regardless of the treatment. The consistency of the findings suggests that the success rate at 12 months is predictive of the success rate at 18 months.

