9.8. Efficacy Analysis

9.8.1. Primary Efficacy Analysis

Primary Efficacy Endpoint

The primary efficacy endpoint is the. success or failure, at 12 months after the final treatment intake. The patient's treatment will be a success if there is no evidence of trypanosomes in any bodily fluid, and the WBC count in the CSF is $\leq 20/\mu$ L. Patients with no parasitological evidence of relapse, but with a CSF WBC count > 20/µL or who, in the opinion of the Investigator, require rescue treatment, will be considered to be probable relapses and therefore as failures. Death due to any cause or use of rescue medication will be considered as a relapse, i.e. a failure. A patient who attends the follow-up visit at 12 months or later and who

refuses to undergo lumbar puncture, but who has no signs or symptoms of HAT and for whom the outcome was assessed as favourable at the last assessment will be considered as a probable cure, i.e. a success, unless signs of relapse are detected on any assessment up to 18 months.

Primary Analysis

The primary analysis will be performed on the ITT population.

The primary endpoint is the success or failure of treatment, as defined above.

The primary analysis of success or failure will be performed at 12 months of follow-up.

The primary test is an exact test derived from the exact confidence interval (CI) of the success rate at 12 months.

Two sets of statistical hypotheses will be tested simultaneously:

 H_{0A} : the true success rate is equal to or less than 80%, which is considered to be unacceptable.

H_{1A}: the true success rate is greater than 80%.

 H_{0B} : the true success rate is equal to or greater than 92%, which is the target or expected success rate for fexinidazole.

H_{1B}: the true success rate is less than 92%.

If H_{0A} is rejected, then the success rate is significantly greater than 80% and the estimated rate is consistent with a rate of 92%. In this case, H_{0B} is automatically accepted, but not necessarily true.

If H_{0B} is rejected, then the success rate is significantly less than the target of 92%, and the estimated rate is consistent with the unacceptable rate of 80%. In this case, H_{0A} is automatically accepted, but not necessarily true.

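### Section 9.2's primary imputation, read literally, fails children first assessed again after month 12, whereas 2.2.1 lets the later assessment decide; no section takes precedence

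*Protocol*

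**What the plan says.** Three places in the protocol say how to classify a child who has no lumbar puncture at month 12.

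- **Section 2.2.1 (endpoint definition).** The success provision opens with "Patients lost to follow-up and retrieved after 12 months" and also covers puncture refusers. Such a child is a success if free of signs suggesting HAT, or if the symptoms clearly have another cause, provided the last available assessment was favourable. If a puncture or physical examination is done later, "the outcome at the latter visit will prevail over that at 12 months". Children never retrieved are failures.
- **Section 9.2 (primary imputation).** Success is imputed to a child who came to the 12-month visit, refused its puncture, had no signs then, reported no relapse symptoms later and was favourable at the last assessment. Then: "If these criteria are not fulfilled, the patients will be considered as treatment failures". Children lost from month 12 onwards also count as failures.
- **Section 9.8.1 (primary analysis).** The success wording begins "A patient who attends the follow-up visit at 12 months or later and who" and is limited to children who refuse the puncture. It requires no signs and a favourable last assessment, and it lapses if relapse is detected up to month 18. Death and use of rescue medication are failures.

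Section 9.2 adds two further methods. The second consists in "imputing failure if there is no lumbar puncture at 12 months or later". The third imputes nothing, and it is the only one for which 9.2 says that a later status overrides a missing intermediate one.

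**The concern.** The primary result is a single count of successes in an open-label, single-arm study: 109 of 125 passes and 108 fails. If the protocol classifies the same child both ways, that count is not uniquely defined. Whoever settles the question later may do so knowing the outcomes.

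The sensitivity analysis is affected too. On the literal reading of 9.2, a child who misses month 12 and has a clean puncture at month 18 fails the primary method but passes the second method, which requires only a puncture at month 12 or later. For that child the additional method is more lenient than the primary.

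**Working it through.** **1. The plan's own figure.** The inputs come from 9.1 and 9.8.1: n = 125, a pass mark of 109 successes, H0A that "the true success rate is equal to or less than 80%, which is considered to be unacceptable", and H0B that "the true success rate is equal to or greater than 92%, which is the target or expected success rate for fexinidazole". Section 9.1 says the probability of rejecting H0A "is 97.5% if the true success rate is 92% with a one-sided type-I error of 0.025".

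- Power: P(Bin(125, 0.92) ≥ 109) = 97.8%. This agrees with the stated 97.5%, which 9.1 says is slightly exceeded.
- Attained one-sided alpha: P(Bin(125, 0.80) ≥ 109) = 0.0243, below 0.025.
- Exact 95% lower limits: 80.05% at 109/125 and 79.12% at 108/125.

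The sample size is sound, and one child decides the result at the boundary.

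**2. Worked cases.** No child here has a 12-month puncture. In A to C and E the last earlier assessment was favourable. No child dies or receives rescue treatment.

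| Case | 2.2.1 | 9.2 primary, literal | 9.8.1 |
|---|---|---|---|
| A. Misses month 12; well at month 18, refuses puncture | success | failure | success |
| B. Misses month 12; clean puncture at month 18 | success | failure | not addressed |
| C. Misses month 12; well on examination at month 18, no refusal recorded | success | failure | outside its success wording |
| D. Attends month 12 with signs, refuses; clean puncture at month 18 | success | failure | not addressed |
| E. Attends month 12, refuses; well then and later | success | success | success |

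The disagreement is between 9.2 and 2.2.1 in cases A to D.

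**3. Who is in the disputed group.** Table 2 allows the 12-month visit at 10-16 months after end of treatment and the 18-month visit at 17-21 months. A child who comes back at 13-16 months can count as a 12-month attender. The group is therefore mainly children first seen again after 16 months, plus case D.

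**4. What it could do to the result.** The documents do not give the number of disputed children, k, so it is an assumption here, ranging from 1 to 6. Let the other 125 − k children succeed independently at 92%.

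- All k counted as successes: P(Bin(125 − k, 0.92) ≥ 109 − k).
- All k counted as failures: P(Bin(125 − k, 0.92) ≥ 109).

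| k | counted as successes | counted as failures |
|---|---|---|
| 1 | 98.0% | 96.1% |
| 2 | 98.1% | 93.3% |
| 4 | 98.4% | 83.0% |
| 6 | 98.6% | 64.5% |

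With 90% in the rest and k = 4, the pair is 90.5% and 56.4%. For scale, 125 × 0.92 = 115 expected successes, which is 115 − 109 = 6 above the pass mark.

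**5. The other direction.** Suppose the true rate under the 9.2 rule is 80% and k failures are counted as successes, so that the rate becomes 0.80 + k/125. The chance of passing rises from 2.4% to 3.9% (k = 1), 6.2% (k = 2), 9.5% (k = 3) and 14.0% (k = 4).

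**The case against.** The best defence is that 9.2 applies only when the 12-month outcome is missing, and that under 2.2.1 a later puncture or examination supplies that outcome. The sentence failing children lost from month 12 onwards would be redundant if every non-attender had already failed, and the second method's acceptance of a late puncture fits this reading. Case B would then be a success throughout, and the second method would not be more lenient than the primary.

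This reading is possible, but the protocol does not state it and other text points away from it. Section 9.2 classifies 12-month refusers whom 2.2.1 has already classified, so it is not written as a residual rule. It also gives precedence to a later status only in its third method. The ambiguity stands.

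Other objections limit the point, and they stand:

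- A reader might infer that three rules give three different answers. They do not. In case A, 2.2.1 and 9.8.1 agree against 9.2, and for a later puncture 9.8.1 is silent, which is not a contradiction.
- A reader might infer that refusal of puncture, which section 14.2.3 permits, drives the problem. A well child with a favourable history who attends month 12 and refuses is a success under all three sections (case E).
- A reader might infer that the sensitivity analyses no longer bracket the primary at all. The second method is still stricter for attending refusers who never have a puncture; the reversal is confined to late punctures on the literal reading.
- The visit window, off-site follow-up (6.4) and the permanent-address criterion (4.2) should keep the group small.
- A SAP is due before database lock (section 9), and a pre-lock committee reviews the success and failure rules (10.2). These reduce the risk of a choice made after outcomes are known but do not remove it, because the study is open-label and that committee consists of people involved in its conduct and data processing.

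**Conclusion.** The point holds in a limited form. On its wording, 9.2's primary imputation fails children whom 2.2.1 counts as successes on a later assessment; 9.8.1 sides with 2.2.1 for late-seen refusers, and no order of precedence is given. This is not a detail left to the SAP, since the protocol itself fixes the primary outcome in ways that differ.

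The effect depends on an unknown k. At 92% in the remaining children, the gap between the two classifications is about 2 percentage points in the chance of study success at k = 1 (98.0 − 96.1), 15 at k = 4 (98.4 − 83.0) and 34 at k = 6 (98.6 − 64.5). These figures assume that all disputed children move the same way, so they are the extremes for each k. The documents do not support a claim that the verdict will turn on this, only that it can. The sample size, pass mark and power are unaffected.

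**What to change.** Reconcile 2.2.1, 9.2 and 9.8.1 into one primary-endpoint rule, cross-referenced from all three sections. The rule should:

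1. Apply death and use of rescue medication as failures first, as 9.8.1 already states. If a 12-month puncture result were read first, a child rescued before month 12 with a clean puncture would become a success, against 9.8.1.
2. Say explicitly whether a puncture or examination after month 12 counts as the observed outcome before any imputation, and up to what visit window. This should also settle the tension within 2.2.1, where a refuser with an earlier unfavourable outcome is a failure but a later visit prevails.
3. Keep 2.2.1's provision for symptoms due to another cause, or justify dropping it.
4. Count children never retrieved as failures.

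Report the narrower 9.2 rule, and a rule that treats absence of a puncture as failure, as named sensitivity analyses, and give the number of children whose classification differs between the rules. The cost is wording in the protocol and SAP before database lock. No new data are needed, and n = 125 and the pass mark of 109 stay as they are.

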6.1. Timing of Assessments

The timing of assessments is summarised in Table 3 (p 95).

- D-15 to D-1: Patient screening with detection of *T.b. gambiense*, pre-treatment of concomitant helminthiasis and/or malaria, if any, and ECG.
- D-4 to D-1: Baseline assessment, laboratory screening.
- D1 to D10: treatment period.
- D10 to D12: sampling for PK analyses.
- D11: EOT visit.
- D13 to D18: EOH visit; if the end of hospitalisation is extended beyond D18, the EOH visit should be performed on D18 and an additional unscheduled visit should be performed at hospital discharge.
- Additional follow-up visit: at 9 weeks after D1, i.e. D64 to D70, for patients who reach this visit starting in mid-December 2014.
- Follow-up visits: at M3, M6, M12 and M18 see Table 2 Theoretical Schedule of Visits and Acceptable Leeway). The timing of these follow-up visits is calculated from D11 (EOT).

Theoretical schedule of visits	Ideal timing of visits	Acceptable leeway*	
EOT visit	D11 after the Start of Treatment (SOT)	Between D11 and D12 after SOT	
	(D1 after EOT)	(D1 or D2 after EOT)	
EOH visit	Between D13 and D18 after SOT (D3 and D8 after EOT)	D18 at the latest	
Week 9 after D1	D64 to D70		
3 months	3 months ± 1 week after EOT	2-4 months after EOT	
6 months	6 months ± 2 weeks after EOT	5-9 months after EOT	
12 months	12 months ± 4 weeks after EOT	10-16 months after EOT	
18 months	18 months ± 4 weeks after EOT	17-21 months after EOT	

Table 2 - Theoretical Schedule of Visits and Acceptable Leeway

* The acceptable leeway for the visits starts on the first day of the period mentioned and ends on the last day of the period mentioned.

For the purposes of the study, patients will be hospitalised from their arrival at the hospital/investigational centre until D18. They will be permitted to leave hospital from D11 onwards, if their clinical status allows it.

Any additional unscheduled visits that may take place must be recorded in the CRF.

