9.8.3. Secondary Efficacy Analyses

- The secondary analysis will be performed on the success rate at month 18.
- determine whether the success rate of treatment with fexinidazole varies depending on the stage of the disease, i.e. stage 1 versus early stage 2 versus late stage 2, using a Fisher exact test to compare the rates observed with the 3 different stages.

If the difference between the 3 stages is significant, then the exact 95% CI of each success rate at 12 months will be calculated, and the stage that is responsible for the heterogeneity will be identified. The stage responsible for the heterogeneity will be separated from the other 2 stages, and the lower limit of the 95% CI of each of the 2 subgroups will be compared to the limit of 75%, which is slight higher than the success rate of melarsoprol at 12 months. A limit lower than 80%, i.e. 75% instead of 80%, was chosen because the sample size in each subgroup will be smaller, which will have an impact on the statistical power of each comparison. The upper limit of the CI of the success rate in patients with stage-1 HAT should be consistent with (greater than or equal to) the rate of 93%, which is the

historical success rate of pentamidine (61). The upper limit of the CI of the success rate in patients with stage-2 HAT should be consistent with the rate of 94%, which is the historical success rate of NECT.

- The correlation between the success rate and the WBC count in the CSF will be estimated using a logistic regression. The WBC count will be a quantitative covariate. Another analysis will be performed using a logistic regression with a random intercept to take into account the centre effect. A trend test will also be performed using the Bartholomew's test. Another analysis will be performed after pooling patients with late stage-2 HAT treated with fexinidazole in the pivotal study with patients in this study. The correlation between the success rate and the baseline WBC count will be adjusted with a logistic regression model using the centre as covariate.
- The time-course of the cumulative rate of definitive failure (from the start
 of treatment to the definitive failure) will be estimated using the KaplanMeier method, and patients lost to follow-up will be considered as
 censures. The success rate at each timepoint will be estimated and
 compared using a Cochran Q-test. The logistic model for repeated
 measures (Glimmix procedure in SAS[®]) will be used to test the time effect

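### Kaplan-Meier censoring at the first missing outcome, not the last assessed one, makes the secondary cumulative-failure curve slightly too low

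*Protocol*

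**What the plan says.** Protocol section 9.2 describes three ways of handling missing outcomes. The third makes no imputation: the success rate at a timepoint uses the patients assessed at that timepoint. If a visit is missed but a later one yields a result, "the status at the subsequent visit will prevail over the status at the intermediate visit". The paragraph ends with the survival-curve rule: "In the Kaplan-Meier approach, the observation is censured at the first missing outcome, provided that all subsequent outcomes are also missing" (the verb is evidently meant as censored).

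Section 9.8.3 is where the curve is planned: "The time-course of the cumulative rate of definitive failure (from the start" of treatment to definitive failure) "will be estimated using the KaplanMeier method, and patients lost to follow-up will be considered as" censored observations. No censoring time is given there, so section 9.2 is the only rule.

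Section 6.1 sets the assessment times: "Follow-up visits: at M3, M6, M12 and M18". Its Table 2 accepts a month-12 visit at any time from 10 to 16 months after the end of treatment.

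**The concern.** A patient should leave the risk set when observation stops. For an outcome ascertained mainly at visits, that is the last visit with a result. The section 9.2 rule moves the censoring time forward to the next visit, the one without a result.

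Take a child found well at month 6, with nothing recorded at months 12 and 18. The child is censored at month 12. By the usual convention, events come before censorings at tied times, so the child is at risk for the month-12 failures. No failure could have been recorded for this child there. In effect the child counts as failure-free through month 12.

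Under non-informative loss the error runs one way: cumulative failure is too low, which flatters the drug in a study without a control group. The curve is one of the planned analyses for the secondary objective on how the success rate changes over time.

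**Working it through.** **The plan's own figures.** The protocol states no figure for the Kaplan-Meier rule. The nearest design figure is in section 9.1: "With a sample size of 125 patients", the probability of rejecting the 80% null "is 97.5% if the true success rate is 92% with a one-sided type-I error of 0.025". With the section 9.8.1 rule of at least 109 successes out of 125, the exact binomial gives a one-sided alpha of 0.0243 and power of 0.978, in line with the stated values. That test uses no Kaplan-Meier estimate.

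**Inputs from the protocol.** N = 125 and a target success rate of 92%, so 8% failure (10 children) by month 12 (section 9.1). Relapse between months 12 and 18 of about 1.2% (section 2.2.1, given for stage 2).

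**Assumptions.** Of the 10 failures, 4 occur by month 6 and 6 between months 6 and 12. A fraction l is lost, independently of outcome, in each of the last two intervals: l = 5%, 10% or 15%. Censorings are tied with the events of the visit concerned.

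**Month 12.** After month 6, 125 − 4 = 121 children are at risk. Of these, 121(1 − l) are assessed at month 12 and 6(1 − l) failures are seen.

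- Censoring at the last assessed visit: h12 = 6(1 − l) / [121(1 − l)] = 6/121
- Censoring at the first missing outcome: h12 = 6(1 − l) / 121

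**Month 18.** The 115 children still failure-free would give 1.2% × 115 ≈ 1.4 failures. So h18 = 1.4/115 = 0.0122 under last-visit censoring and 0.0122(1 − l) under the section 9.2 rule.

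**Cumulative failure.** At month 12 it is 1 − (121/125)(1 − h12). At month 18 it is 1 − (121/125)(1 − h12)(1 − h18).

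| Loss per interval | Month 12 | Month 18 |
|---|---|---|
| Last-visit censoring, any l | 8.00% | 9.12% |
| Section 9.2 rule, 5% | 7.76% | 8.83% |
| Section 9.2 rule, 10% | 7.52% | 8.53% |
| Section 9.2 rule, 15% | 7.28% | 8.24% |

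For example, at 10% loss h12 = 5.4/121 = 0.0446, and 1 − 0.968 × 0.9554 = 7.52%.

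**Whole-number check.** Take 125 children with failures 1, 4, 5 and 1 at months 3, 6, 12 and 18, and 12 children whose outcome is first missing at month 12. Before month 12, 120 are at risk. Last-visit censoring gives 1 − 0.96 × (1 − 5/108) = 8.44%. The section 9.2 rule gives 1 − 0.96 × (1 − 5/120) = 8.00%.

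**Other loss patterns.** With assumed cumulative failure of 0, 1, 4, 8 and 9.2% at the end of treatment and months 3, 6, 12 and 18, and total loss of 2% to 30% spread evenly over the visits or placed at one visit, the section 9.2 rule gave the lower month-12 figure every time. The shortfall ran from 0.04 points (2% lost, spread) to 1.25 points (30% lost, all at month 12).

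**The case against.** **The size rests on an unstated date.** A missed visit has no date, and section 9.2 assigns none. With actual dates and a 10-to-16-month window, month-12 failures would not all be tied with the censorings. The child then counts as at risk only for failures dated on or before the assigned date. This stands: the table gives the tied case and is not an exact prediction. It does not rescue the rule, because any assigned date after the last assessment adds time in which nothing was observed.

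**A missing outcome is not always a missed visit.** Section 9.2 counts a child who attends but refuses lumbar puncture among those with a missing month-12 outcome. Under section 6.4.3 that child would still have an examination and blood and lymph testing. For such children, saying that failure could not be seen is too strong. This stands too: the figures model non-attendance only.

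**The effect is small.** The standard error of an 8% rate with 125 children is √(0.08 × 0.92/125) = 2.4 points, and the largest month-12 shift in the table is 0.72 points, under a third of it. Section 9.8.3 also plans visit-wise rates with a Cochran Q-test and a repeated-measures logistic model, so the objective does not rest on this curve alone.

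**A stronger reading.** A reader might infer that the later-status rule also moves Kaplan-Meier failures back to visits that never took place. The documents do not show this. That sentence follows the description of visit-wise success rates and precedes the separate Kaplan-Meier sentence, and section 9.8.3 times the curve to the definitive failure. If it did apply, it would bring failures forward, against the drug.

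**Conclusion.** The point holds as a small, one-directional error in a stated rule. It is not a detail left open for the SAP: section 9.2 fixes the censoring time, and nothing else in the protocol moves it back to the last assessment. For 5% to 15% loss per interval the curve is low by about 0.2 to 0.7 points at month 12 and 0.3 to 0.9 points at month 18.

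Those figures assume the loss rates, the timing of failures, non-informative loss, non-attendance as the cause of the missing outcome, and censorings tied with events. If loss depends on outcome, that is a separate bias which a different censoring date will not cure.

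A reader might infer that the trial's conclusion is at risk. It is not: the primary analysis counts children who are lost and not retrieved as failures, so the decision rule of 109 successes out of 125 does not depend on the Kaplan-Meier rule.

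**What to change.** Replace the last sentence of the third method in section 9.2 with: *In the Kaplan-Meier approach, a patient whose subsequent outcomes are all missing is censored at the date of the last visit with an assessed outcome.* The SAP should repeat this wording and state whether a visit attended without lumbar puncture counts as assessed.

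Leave the later-status rule for missed intermediate visits as it is. Carrying back only later successes and leaving later failures missing would select on outcome and inflate the visit-wise success rates.

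The cost is one sentence in the protocol and its counterpart in the SAP. No new data, visits or sample-size changes are needed.
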